PROTOCOL STUDY SYNOPSIS					
Title:	Evaluation of the Rotation Medical Bioinductive Implant for Insertional Achilles Tendonopathy				
Study Devices:	Rotation Medical Bioinductive Implant (Cleared for commercial use by the U.S. Food and Drug Administration: K140300; K131637; K131635; K122048)				
Study Design:	Prospective, non-randomized				
Enrollment:	Up to 10 subjects will be treated				
Inclusion Criteria:	 At least 21 years of age Insertional Achilles tendonitis requiring surgery that has failed conservative management, which consist of: A. Shoe modification B. Nonsteroidal anti-inflammatory drugs C. Physical Therapy with/without modalities Chronic Achilles tendon pain lasting longer than 3 months MRI of the ankle within 60 days prior to the study procedure Willing to comply with the prescribed post-operative rehabilitation program Willing to be available for each protocol-required follow-up examination Able to understand the informed consent process, including regulatory requirements such as HIPAA authorization, and document informed consent prior to completion of any study-related procedures 				
	8. Ability to read, understand, and complete subject-reported outcomes in English				
Exclusion Criteria:	 Achilles tendon rupture Previous Achilles tendon surgery on the index ankle Genetic collagen disease History of auto-immune or immunodeficiency disorders History of chronic inflammatory disorders Oral steroid use in last 2 months or injectable steroid use in last 4 weeks History of heavy smoking (> 1 pack per day) within last 6 months Hypersensitivity to bovine-derived materials Hypersensitivity to Polylactic Acid (PLA) and Polyetheretherketone (PEEK) materials Metal implants, fillings, shrapnel, and/or screws Females of child-bearing potential who are pregnant or plan to become pregnant during the course of the study Currently involved in any injury litigation or worker's compensation claims relating to the index ankle Enrolled, or plans to enroll, in another clinical trial during this study that would affect the outcomes of this study History of non-compliance with medical treatment, physical therapy/rehabilitation, or clinical study participation History of cognitive or mental health status that interferes with study participation 				
Study Objective:	To evaluate bioinduction of new tissue and tendon healing after implantation of the Rotation Medical Bioinductive Implant used as adjunct to surgical repair in the treatment of insertional Achilles tendonitis.				

MRI assessment of the following:			
1. Increase in tendon thickness			
2. Integration of induced tissue with the underlying tendon and maturation of			
the induced tissue			
3. Amount of defect fill-in and characteristics of both the filled-in tissue within			
the tendon			
4. Achilles tendon tear rate at surgical site			
1. Safety			
2. Procedure parameters			
3. Recovery			
4. Subject satisfaction			
Baseline			
Procedure			
Post-procedure follow-up: 3 months, 1 year, 2 years			
Rotation Medical, Inc.			
[name]			
[name]			
Datation Madical Inc			
Rotation Medical, Inc.			
[name]			
[name]			

1 INTRODUCTION & RATIONALE

Chronic insertional Achilles tendinopathy is a common ailment in the general population. It is traditionally described as a phenomenon of overuse in both athletic and nonathletic individuals. Non-operative management usually consists of activity and shoe modifications, nonsteriodal anti-inflammatory medications (NSAIDs), and some form of physical therapy, which can be successful. In patients in whom conservative interventions fail, operative intervention is the next step. This intervention intails open detachment and debridement of the diseased Achilles tendon, calcaneal osteotomy, and reattachment of the Achilles. Often the diseased Achilles debridement leaves the tendon compromised in terms of its integrity and the remaining tendon will need augementation with a tendon transfer using the flexor hallucis longus (FHL).

The Rotation Medical Bioinductive Implant is a bioabsorbable device that provides a layer of collagen over injured tendons. This device is indicated for the management and protection of tendon injuries in which there has been no substantial loss of tendon tissue and can be implanted during a the standard open treatment for insertional Achilles tendinopathy. The device was first evaluated in a preclinical study of 23 sheep that was approved by the Colorado State University Institutional Animal Care and Use Committee. The device did not elicit an inflammatory response or a foreign body reaction. Histological analysis confirmed the device was completely absorbed after six months with integration of the new tendinous tissue to the underlying host tendon and a fibrocartilagenous transition zone at the tendon-to-bone insertion site. Tendon thickness at the implant site increased by approximately 2.5 millimeters due to induction of new tendinous tissue and remained stable one year after surgery.

2 DEVICE DESCRIPTION

2.1 DEVICE DESCRIPTION

There are three implantable components in the Rotation Medical Bioinductive ImplantTM (**Figure 1**).

[figure not shown]
Bioinductive implant: The device is made from highly purified reconstituted collagen fibers derived from bovine tendon and manufactured for Rotation Medical, Inc. by Collagen Matrix, Inc. (Oakland, New Jersey, USA). It is contraindicated for use in patients with a history of hypersensitivity to bovine-derived materials and this is an exclusion criterion for study participation. The device is designed to completely absorb within six to 12 months.

Tendon staples: The tendon staples are made from poly(L-lactide-co-D,L-lactide) in a molar ratio of 70% L-lactide to 30% D,L-lactide. Polylactide materials have been used in a variety of medical devices, such as bone anchors, bone pins, screws, plates, and spinal fusion cages. The tendon staples are designed to completely absorb within approximately 12 months.

Bone staples: The bone staples are made from polyetheretherketone (PEEK), which is a common polymer used for bone anchors in orthopedic surgery. The bone staples are not bioabsorbable.

The Rotation Medical Rotator Bioinductive Implant has been cleared by the U.S. Food and Drug Administration (FDA) [K140300; K122048; K131635; K131637]. The purpose of this post-market study is to collect and analyze outcomes data under a common protocol.

Figure 1: Rotation Medical Implantable System Components

The tendon and bone staplers used to affix the bioinductive implant to tendon tissue and the calcaneus respectively are shown in **Figure 2**. These are designed as single-use devices.

Figure 2: Rotation Medical Single-Use Disposable Staplers

2.2 PRINCIPLES OF OPERATION

No investigational devices or procedures will be used in this post-market study and all devices will be used according to their indications for use. Operation, indication, and instructions for use are described in the Instructions for Use (IFUs).

3 STUDY OBJECTIVE

To evaluate bioinduction of new tissue and tendon healing after implantation of the Rotation Medical Bioinductive Implant used in the treatment of insertional Achilles tendonapathy.

4 STUDY DESIGN

This is a prospective, non-randomized, single-arm study conducted under a common protocol designed to evaluate long-term outcomes following open treatment and implantation of the Rotation Medical Bioinductive Implant to treat insertional Achilles tendinopathy.

4.1 SAMPLE SIZE

Up to 10 subjects will be enrolled and treated with the Rotation Medical Bioinductive Impant at Union Memorial hospital and the associated Surgery Center.

4.2 STUDY DURATION

Enrollment is anticipated to take up to 12 months and all subjects will be followed for two years after surgery. Therefore, the overall study duration is estimated to be 36 months.

4.3 PRIMARY OUTCOME MEASURES

4.3.1 Increase in Tendon Thickness

Achilles tendon thickness will be measured pre-operatively (baseline) and the total thickness of the tendon and any newly induced tissue at the implant site will be measured at each follow-up visit using magnetic resonance imaging (MRI). The mean (\pm SD) change in post-operative Achilles tendon thickness will be calculated at each follow-up interval.

4.3.2 Integration and Maturation of New Tissue

Integration and maturation of the newly induced tissue will be assessed by MRI at each post-operative follow-up. This outcome will assess, at a minimum, the following characteristics of the newly induced tissue: (i) presence or absence of a clear boundary between the device and the underlying tendon; (ii) maturation of newly induced tissue to resemble characteristics of underlying tendon tissue (versus debris, artifact, or calcification).

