7.7 FOLLOW-UP ASSESSMENTS

All subjects will undergo post-operative study assessments at 3 months, 1 year, and 2 years after discharge from the study procedure as described below and summarized in **Table 7.1**.

7.7.1 3-Month (± 15 Days) Follow-Up

- 1. Perform an MRI per the Sponsor Imaging guidelines.
 - Provide the Sponsor with a de-identified digital copy of, or access to, the MRI
- 2. Clinical Assessment
- 3. Record prescription medications
 - Record any prescription medications the subject is taking at the time of the follow-up visit to treat his/her index Achilles.
- 4. Record any new adverse events and update the status of any ongoing, previously-reported adverse events.
- 5. Report any new revision/additional Achilles surgeries performed on the index Achilles

7.7.2 1-Year (\pm 45 Days) Follow-Up

- 1. Perform an MRI per the Sponsor imaging guidelines.
 - Provide the Sponsor with a de-identified digital copy of, or access to, the MRI.
- 2. Clinical assessment
- 3. Administer the recovery/satisfaction questionnaire (VISA-A)
- 4. Record prescription medications.
 - Record any prescription medications the subject is taking at the time of the follow-up visit to treat his/her index Achilles.
- 5. Record any new adverse events and update the status of any ongoing, previously-reported adverse events.
- 6. Report any new revision/additional Achilles surgeries performed on the index Achilles.

7.7.3 2-Year (\pm 90 Days) Follow-Up

1. Perform an MRI per the Sponsor imaging guidelines.

- Provide the Sponsor with a de-identified digital copy of, or access to, the MRI.
- 2. Clinical assessment
- 3. Administer the recovery/satisfaction questionnaire.
- 4. Record prescription medications.
 - Record any prescription medications the subject is taking at the time of the follow-up visit to treat his/her index Achilles.
- 5. Record any new adverse events and update the status of any ongoing, previously-reported adverse events.
- 6. Report any new revision/additional Achilles surgeries performed on the index Achilles.

The results of all follow-up assessments will be documented on their respective CRFs. Each reportable adverse event (**Section 4.1.1**) will be documented on an Adverse Event CRF.

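### Integration item (i) scores a boundary with an implant designed to be absorbed by 12 months, so on late scans it cannot by itself separate integrated new tissue from no new tissue

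*Combined protocol and SAP*

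**What the plan says.** Integration and maturation form one of the primary outcomes. Section 4.3.2 sets the timing: "Integration and maturation of the newly induced tissue will be assessed by MRI at each post-operative follow-up". It introduces two minimum items as describing "the following characteristics of the newly induced tissue". Item (i) is the "presence or absence of a clear boundary between the device and the underlying tendon". Item (ii) asks whether the new tissue has matured towards the appearance of tendon, as opposed to debris, artefact or calcified material. No scale is given for item (ii), no rule for combining the two items, and no instruction for a scan on which no new tissue is seen.

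On absorption, section 2.1 says of the collagen component: "The device is designed to completely absorb within six to 12 months". Section 1 reports from the sheep study: "Histological analysis confirmed the device was completely absorbed after six months".

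On timing, section 7.7 provides for "post-operative study assessments at 3 months, 1 year, and 2 years after discharge from the study procedure". Table 7-1 sets windows of 15, 45 and 90 days either side.

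The synopsis describes the same outcome differently: there, the thing that integrates with the tendon is the induced tissue, not the device. Section 5 plans chi-square analyses of the integration and maturation indices at each visit and does not restrict them to subjects in whom tissue was seen.

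**The concern.** The study objective is to evaluate whether the implant induces new tissue. Item (i) names the implant itself, which is meant to disappear during follow-up. Once it has gone, there is nothing left to form a boundary with the tendon, so the item stops carrying information about the tissue. A subject in whom tissue formed and merged with the tendon, and a subject in whom none formed, would both be read as having no clear boundary.

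The time course adds to the difficulty. Absorption alone would move a subject from boundary at 3 months to no boundary at 2 years, and that pattern is easily reported as progressive integration. The study has one arm, so no comparison group would show the boundary vanishing without induction. With at most 10 subjects, a few such readings would change the reported proportion materially.

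**Working it through.** The plan gives no sample-size, power or precision figure for this outcome, so there is none to reproduce. The check compares visit windows with absorption time and then works through what item (i) records.

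**Step 1: windows against absorption.** Inputs are the visit times and windows (section 7.7, Table 7-1) and the absorption range (section 2.1). One month is 365.25/12 = 30.44 days. Absorption should be complete between 6 × 30.44 = day 183 and 12 × 30.44 = day 365.

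| Scan | Window in days | In months | Position relative to day 183–365 |
|---|---|---|---|
| 3 months | 91.3 ± 15 = 76 to 106 | 2.5 to 3.5 | Wholly before; the window closes 183 − 106 = 77 days before the earlier limit |
| 1 year | 365.25 ± 45 = 320 to 410 | 10.5 to 13.5 | Straddles the later limit; residual implant is possible from day 320 to 365 |
| 2 years | 730.5 ± 90 = 640 to 820 | 21 to 27 | Wholly after; 640 − 365 = 275 days (about 9 months) to 820 − 365 = 455 days (about 15 months) past the later limit |

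The bone staples are not absorbable, but section 2.1 has them fixing the implant to the calcaneus, so they do not supply a lasting boundary with the tendon.

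**Step 2: what item (i) records once the implant is absorbed.**

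| True state | Item (i) read literally | Item (i) if the reader takes the device to mean the new layer |
|---|---|---|
| Tissue induced and integrated | No boundary | No boundary |
| Tissue induced, not integrated | No boundary | Boundary |
| No tissue induced | No boundary | No boundary, or not assessable if the reader chooses to say so |

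Read literally, all three states look alike. The generous reading separates the second row. It separates the third only if readers adopt a category that section 4.3.2 does not provide.

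**Step 3: illustration of size.** These inputs are assumptions, not figures from the documents: 10 subjects, all implants absorbed, *k* subjects with induced tissue, a share *q* of those integrated, and the generous reading with no not-assessable category. Then

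- subjects read as no boundary = (10 − *k*) + *q* × *k*
- subjects truly integrated = *q* × *k*
- excess = 10 − *k*

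| *k* | *q* | Read as no boundary | Truly integrated |
|---|---|---|---|
| 0 | any | 10 + 0 = 10 | 0 |
| 5 | 0.5 | 5 + 2.5 = 7.5 | 2.5 |
| 5 | 1.0 | 5 + 5 = 10 | 5 |
| 10 | 0.5 | 0 + 5 = 5 | 5 |

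The excess equals the number of subjects without induced tissue, so it is zero if every subject forms tissue. Under the literal reading the first count is 10 in every row.

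**The case against.** The strongest reply is that item (i) is loosely worded, not wrongly designed. Its own lead-in concerns newly induced tissue, and so does the synopsis, so a sensible reader would take the device to mean the new layer at the implant site. That is a fair account of the intent. It does not remove the problem, because step 2 shows that even then a scan without new tissue has no defined score.

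A second reply is that the protocol nowhere equates no boundary with integrated. That is correct, and the finding must be limited accordingly. It remains the natural reading of an item placed under integration, and leaving the direction unstated protects nobody.

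Third, other measurements bear on whether tissue formed. A scan with no new tissue can hardly show it maturing under item (ii). Section 4.3.1 measures total thickness, and the synopsis lists defect fill-in. This stands in part. None of these is linked to item (i), however, and the debridement and optional FHL transfer described in section 7.5 can also change thickness.

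Fourth, the items are only a minimum, and scans follow an MRI guideline that is not among the documents. It may define reading categories, which limits how certain one can be.

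A reader might infer more: that induction failure and success receive the same result on the whole primary outcome, or that the study would report 100% integration with no induction. The documents do not support either. The indistinguishable readings concern item (i) alone, the scoring direction is not written down, and the 10-out-of-10 figure follows from the assumptions in step 3.

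**Conclusion.** The concern holds for item (i). If absorption proceeds as designed, the item cannot by itself distinguish integrated induced tissue from no induced tissue anywhere in the 2-year window. The same applies at 1 year to subjects whose implant has already gone; how many that will be cannot be derived from the documents. A shift from boundary to no boundary over follow-up could reflect absorption only.

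This is more than missing detail, because the item as written measures something other than the outcome that the synopsis names. The size depends on how many subjects form no tissue, which is unknown. The conclusion rests on the stated absorption range, which is a design statement and may not hold in every patient, and on reading the protocol without its imaging guideline. Feasibility status explains the absence of power; it does not make an item informative. The problem can be corrected with the scans already planned and should be settled before images are read.

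**What to change.** In section 4.3.2 and on the MRI reading form:

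1. At each MRI, first record induced tissue at the implant site as *present*, *absent*, or *not distinguishable from residual implant*.
2. Reword item (i) as the boundary between the newly induced tissue and the tendon beneath it, scored only where tissue is recorded as present. State that no clear boundary there counts as integrated.
3. Report the integration proportion over all subjects with a readable scan at that visit. Count *absent* as not integrated. Show *not distinguishable* as its own category, kept in the denominator and not counted as integrated.
4. Note that the 3-month scans precede the stated absorption period and may show implant as well as tissue.
5. Check that the MRI guideline uses the same categories.

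Which visit carries the conclusion is for the sponsor to decide; the repair does not depend on it.

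The cost is a wording change and one added field on the form, with no extra scan or subject. A small downside is that early integration results may look less favourable.

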4.3.3 Tear Rate

Tear rate following Achilles surgery will be assessed at each follow-up visit using MRI.

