4.4.2 Procedure Parameters

The following procedural parameters will be recorded on all subjects:

- 1. Device implant time: Mean (\pm SD) implant time defined as follows:
 - Open procedure: Time from introduction of the bioinductive implant into the surgical field to completion of the last staple
- 2. Procedure technical success: The proportion of subjects where the device was successfully delivered and affixed to target tendon location.
- 3. Device implant position: An intra-operative photograph(s) or video recording showing the implant location of the device and all tendon and bone staples will be obtained.

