5 STATISTICAL ANALYSIS PLAN

This is an initial feasibility study and not powered to address the hypotheses. Changes in tendon thickness over the time of the follow up visits will be assessed by a Repeated Measures ONEWAY ANOVA with a post hoc Scheffe. Indices of new tissue integration and maturation at each follow up visit will be assessed by Chi Square analyses.

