12 RISKS AND BENEFITS

12.1 RISKS AND RISK MITIGATION

Study patients will be informed of all known potential side effects and complications associated with the study assessments and study procedure prior to enrollment in the study.

There are no known incremental risks to the subject for participating in the study. The risks associated with participating in this study are the same as if the patient is treated outside of the study using the same commercially-available device and include the following potential risks of Achilles Tendinopathy surgery performed under general or regional anesthesia:

- Tissue inflammation
- The need for repeated surgery because tendons do not heal properly or tears
- Pain or stiffness that won't go away
- Fever and/or infection
- Complication from anesthesia
- Nerve or blood vessel damage
- Adverse reaction to device

In addition, subjects will be required to undergo MR imaging. MRI is generally a well-tolerated procedure and there is no ionizing radiation involved with MR imaging. The potential risks are minimal and include claustrophobia, coil element heating and peripheral nerve stimulation, although the latter two are considered highly unlikely, given that the subjects will be imaged within preset safety guidelines to eliminate peripheral nerve stimulation. Coil element heating ranges from a mild sensation of heat to a potential burn. This is considered highly unlikely, as the coils have all undergone extensive testing and clinical use, and special pads are placed surrounding all contact points.

All Investigators will undergo training and subjects will be screened and evaluated for medical histories/conditions that may compromise safe, successful completion of any of the study assessments or performance of the device. Subjects with a known hypersensitivity to bovine-derived materials will not be enrolled in the study.

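### The primary tear rate counts only what a scheduled MRI shows, so a tear revised between scans falls outside it; a cumulative per-subject proportion should be added

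*Combined protocol and SAP*

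**What the plan says.** Section 4.3.3, under the primary outcome heading, consists of one sentence: "Tear rate following Achilles surgery will be assessed at each follow-up visit using MRI". This gives the method and the timing. It gives no denominator, does not say whether the rate is per visit or cumulative, and has no rule for a missing scan or a revised tendon.

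Other outcomes do have a stated summary. For thickness, Section 4.3.1 says that the mean "change in post-operative Achilles tendon thickness will be calculated at each follow-up interval". Section 4.4.2 defines technical success as "The proportion of subjects where the device was successfully delivered and affixed to target tendon location". Section 5 plans a repeated-measures ANOVA for thickness and then says "Indices of new tissue integration and maturation at each follow up visit will be assessed by Chi Square analyses". It does not mention tear rate.

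The plan expects that some tendons may need further surgery. Section 12.1 lists as a risk "The need for repeated surgery because tendons do not heal properly or tears". Section 7.7 tells sites at each visit to "Report any new revision/additional Achilles surgeries performed on the index Achilles", and Section 7.9 asks them to try to obtain the operative notes. Surgery to correct a problem is a serious adverse event under Section 8.2, and Section 4.4.1 plans rates by event type. Section 7.8 records unscheduled Achilles-related visits. Under Section 7.11 a subject leaves the study at withdrawal or loss to follow-up.

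The synopsis has a list of four MRI items. One begins "Amount of defect fill-in and characteristics of both the filled-in tissue within" and another is "Achilles tendon tear rate at surgical site". Section 4.3 has no fill-in outcome and does not limit tears to the surgical site.

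**The concern.** Under Section 7.5 every tendon is detached, debrided and re-attached, so failure of that repair is a main result even in a small feasibility study. A rate tied to three scheduled scans describes the state of the tendon on those days. It does not tell the reader how many subjects had a tear after surgery.

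The two quantities part company when a tear is repaired. A tear that arises and is revised between scans may never appear on a study MRI. A tear that was seen and then revised is gone from the next visit's rate. Both effects lower the visit rate relative to the share of subjects who ever tore. The subjects affected are those with the worst course, and the records that would identify them are collected but not connected to the outcome.

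**Working it through.** The plan states no tear rate, so there is no figure to reproduce. The check is how far the visit rate and the per-subject proportion can differ.

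**Inputs.** Up to 10 subjects (Section 4.1). MRIs at 3 months ±15 days, 1 year ±45 days and 2 years ±90 days (Table 7-1), taken here as days 91, 365 and 730. All tear and missing-scan counts below are assumptions.

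**Time between scans.**
- 3 months to 1 year: planned 365 − 91 = 274 days; shortest (365 − 45) − (91 + 15) = 214; longest (365 + 45) − (91 − 15) = 334.
- 1 to 2 years: planned 730 − 365 = 365 days; shortest (730 − 90) − (365 + 45) = 230; longest (730 + 90) − (365 − 45) = 500.

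These gaps leave time for a tear to occur and be revised without a study scan in between.

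**Effect on the rate.** Assume n = 10, one tear, all scans done, and a revised tendon that reads as intact.

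| Case | Measure | 3 months | 1 year | 2 years |
|---|---|---|---|---|
| A: tear arises and is revised between 3 months and 1 year | Visit rate as written | 0/10 | 0/10 | 0/10 |
| | Visit rate, unrevised tendons only | 0/10 | 0/9 | 0/9 |
| | Cumulative per subject | 0/10 | 1/10 | 1/10 |
| B: tear seen at 3 months, then revised before 1 year | Visit rate as written | 1/10 | 0/10 | 0/10 |
| | Visit rate, unrevised tendons only | 1/10 | 0/9 | 0/9 |
| | Cumulative per subject | 1/10 | 1/10 | 1/10 |

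Exact (Clopper-Pearson) 95% limits for x of n are the 0.025 quantile of Beta(x, n − x + 1) and the 0.975 quantile of Beta(x + 1, n − x). The lower limit is 0 when x = 0.
- 0/10 = 0% (0 to 30.8%)
- 0/9 = 0% (0 to 33.6%)
- 1/10 = 10% (0.3 to 44.5%)

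One subject is 1/10 = 10 points at n = 10, and 1/8 = 12.5 points if only 8 are treated.

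**Missing scans.** Take case A and let two of the other nine subjects, with no documented tear, miss the 2-year MRI. The visit rate among unrevised, scanned tendons is 0/(10 − 1 − 2) = 0/7 = 0% (0 to 41.0%). Cumulatively there is one documented tear and two subjects of unknown status. The bounds are 1/10 = 10% (0.3 to 44.5%) with both counted as untorn, and (1 + 2)/10 = 30% (6.7 to 65.2%) with both counted as torn.

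**Could it arise?** The chance of at least one tear among 10 is 1 − (1 − p)^10, which is 18%, 40%, 65% and 89% for assumed true rates p of 2%, 5%, 10% and 20%. These figures are ceilings on the chance that the problem occurs through revision, since the tear must also be revised.

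**The case against.** The wording of Section 4.3.3 points to a by-visit rate, and a point-in-time MRI measure is legitimate. That it can be lower than a cumulative proportion is a property of the measure. This stands, and it is why the visit rate should be kept. It does not supply a denominator or a rule for revised tendons, and it leaves the primary outcome silent on how many subjects tore.

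The plan also places several descriptive summaries in Section 4, so absence from Section 5 alone proves little. That is fair, but Section 4.3.3 names no summary beyond the word rate. As Section 5 describes an unpowered feasibility study, no hypothesis test of tear rate is called for.

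Three stronger readings are tempting, and the documents do not support them.
- A reader might infer that tears between scans go unreported. They do not: a revision is recorded under Sections 7.7 and 7.9 and is a serious adverse event under Section 8.2. Among ten subjects it would be visible. What is missing is the link to the primary outcome, and that follows from silence, not from a stated rule of exclusion.
- A reader might infer that no tear definition exists. MRIs follow a sponsor imaging guideline that is not among the documents, and a definition may be there.
- A reader might infer selective reporting from the fill-in mismatch. The label of the synopsis list is not visible in the public text and the fill-in item reads as incomplete, so its status as a primary outcome is inferred from the list's match with Section 4.3. The two descriptions of tear rate can also be read together. The mismatch needs reconciling, and nothing more can be concluded from it.

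**Conclusion.** The point holds as a modest improvement that costs little. Followed as written, the primary tear rate omits a tear revised between scans and falls back after a tear is revised, so it can understate the share of subjects who tore. In the assumed example the difference is 0/10 against 1/10, or 10 points for each such subject at n = 10. The exact intervals overlap heavily, and the plan has no threshold that this difference would cross.

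The size rests on assumed event counts and on a revised tendon reading as intact at later scans. The direction rests only on the wording of Section 4.3.3 and on the absence of any link from the revision, adverse event and unscheduled-visit records.

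**What to change.** In Section 4.3.3 and Section 5:

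1. Keep the per-visit MRI rate. Its denominator is the subjects with a readable MRI of an unrevised tendon at that visit. List post-revision MRIs separately.
2. Add, by each visit, the cumulative proportion of treated subjects with any documented post-operative tear of the index Achilles, with an exact 95% CI. Sources are study MRI, the operative note of a revision, an adverse event report or an unscheduled visit. Several sources are needed because Section 8.4 limits non-serious events to those judged related to the device or procedure.
3. Do not count a subject with no documented tear and no MRI at that visit as untorn. Report the number unknown, and the bounds with all unknown counted as untorn and all as torn. The proportion in item 2 equals the lower bound, so the upper bound should always be shown beside it.
4. Make the synopsis and Section 4.3 agree on defect fill-in and on whether tear rate is limited to the surgical site. If fill-in is kept, give it a descriptive summary from the MRIs already planned.

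If the imaging guideline defines a tear, a reference to it in Section 4.3.3 is enough.

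**Cost.** No new visits or scans are needed, only wording and slightly more analysis. Fill-in may add one item to the MRI reading. The cumulative figure depends on operative notes that sites are asked only to try to obtain, and it may look less favourable than the visit rate.
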